## Aims and Hypotheses

The primary aims of this study are:

1. To provide clear open-label evidence that a standard course of TMS therapy can be effective for patients who have a diagnosis of bipolar depression and are currently on mood stabilizing medication.
2. To investigate the safety of TMS in a population at risk for activation from neuromodulation. In particular to observe if these patients are at risk for changing from a depressive state to a mixed or manic state.

Specific Hypotheses are that:

1. TMS will provide effective antidepressant treatment in patients with bipolar depression both type I and II.
2. TMS will show a shorter time to response in bipolar depressed patients compared with the available data in unipolar depressed patients.
3. TMS can be safely given in bipolar depression without inducing a manic or mixed episode switch in patients who are receiving adequate concurrent mood stabilizing medication.

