### **Study Overview and Hypotheses**

We propose to screen patients with bipolar depression I or II, who are already on acceptable mood stabilization. They may or may not be on antidepressants at the time of screening but subjects on antidepressants would be taken off them before completing the screening phase. Those patients who have a depression of at least moderate severity without significant symptoms of activation or mania will be started on a course of open label TMS treatment of up to 35 sessions. Safety and efficacy assessments will be done weekly. Patients will complete a course of treatment when they meet remission criteria (MADRS score < 10) or at the end of 30 treatments, whichever comes first. Patients who are still judged to be improving between treatment 25 and treatment 30 will be eligible to complete up to five additional treatments as the discretion of each site's principal investigator.

Patients who meet response criteria (MADRS score decreases by at least 50%) will complete the full course of 30 to 35 TMS sessions. Patients will be withdrawn for safety concerns, particularly the onset of activation suggestive of mania or a mixed state.

Patients who meet response or remission criteria will be followed monthly for up to six months to evaluate the durability of response. They will be on standard mood stabilizing medications and psychotherapy per their clinician's discretion.

The primary study hypotheses are:

1. TMS will provide effective antidepressant treatment in patients with bipolar depression both type I and II.
2. TMS will show a shorter time to response in bipolar depressed patients compared with the available data in unipolar depressed patients.
3. TMS can be safely given in bipolar depression without inducing a manic or mixed episode switch in patients who are receiving adequate concurrent mood stabilizing medication

The secondary hypothesis is:

1. The majority of treatment responders will show adequate durability of response with remitters showing better durability.

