### Phase II: Open Label TMS Treatment

Once study patients are on stable medication and it is confirmed that they meet the entry criteria for Phase II they will begin a standard course of five times a week TMS treatment for six weeks. They will be assessed at each treatment visit for side effects, concomitant medication use, and once per week for severity of depression and evidence of any symptoms suggestive of mania or agitation. Any suggestion of mania or activation will be assessed by the study physician who will evaluate to determine if the subject can remain in the study or needs other intervention to manage emerging symptoms.

The MADRS, the 17-item Hamilton Depression Rating Scale (HAM-D17), the Quick Inventory of Depressive Symptomatology (Self-Report) (QIDS-SR16), the

YMRS, the C-SSRS (Columbia Suicide Severity Rating Scale) and CGI-S will be performed once per week. The CGI-Improvement Scale (CGI-I) will be done weekly starting at Visit 3. Treatment will continue until remission criteria is reached (MADRS score <10) or 30 treatments have occurred, whichever comes first. If improvement is continuing between treatment 25 and 30, treatments may be extended up to 35. Patients who are discontinued due to onset of manic or mixed symptoms will be followed until resolution of these symptoms. Patients who meet response criteria (MADRS score drops by at least 50%) or remission criteria will be followed in Phase III.

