### **Inclusion and Exclusion Criteria – Phase II**

Patients must meet fulfill all of the following inclusion criteria in order to enter Phase II of the study:

1. Must be at least 18 years old.

2. Must meet **DSM-5** criteria for bipolar (either I or II) depression by clinical interview and M.I.N.I. The duration of the current depressive episode must be at least 4 weeks and no longer than 3 years in length.
3. Should have a MADRS score of at least 20 at screening, an YMRS score of less than 12 and a CGI score of at least 4.
4. Must have signed the informed consent document and have a level of understanding sufficient to provide informed consent and to communicate with the investigator and site personnel.
5. Must be on a mood stabilizer acceptable to the study physician which is consistent with their diagnosis. The mood stabilizer must be at a stable dose for at least four days before starting TMS treatment.
6. If female of childbearing potential, patients must
  - a) have a negative urine pregnancy test at screening, and
  - b) not be nursing or planning a pregnancy, and
  - c) be on a medically acceptable method of birth control acceptable to the principal investigator.

Choices of contraception that meet the study requirements are

- Intrauterine device
- Hormonal contraception (estrogen-containing birth control pills, Vaginal ring, patch, injections or implants)
- Latex condom with spermicide
- Diaphragm with spermicide
- Cervical cap with spermicide

Females of childbearing potential who are abstinent can enroll in the study.

Patients will *not* be enrolled in Phase 2 of the study if they meet any of the following exclusion criteria:

1. May not be directly affiliated with Sheppard Pratt Clinical Research Programs or be immediate family of Research Programs personnel.
2. Must not have another primary Axis I diagnosis.
3. The subject must not have stopped an antidepressant less than two weeks before starting TMS treatment or unable to discontinue antidepressant therapy.
4. Should have no previous history of psychosis or substance dependence or abuse within the six months prior to Screening

5. Presence of an Axis II disorder felt by the investigator to potentially interfere with study compliance would exclude a potential participant.
6. Should not have prior intolerance of TMS or significant lack of response to adequate trials of TMS.
7. Should not have a lifetime history of lack of response to ECT or VNS.

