### **Patient Withdrawal**

Patients will be told verbally and in the informed consent that they have the right to withdraw from the study at any time without prejudice or loss of benefits to which they are otherwise entitled.

The investigator may discontinue a patient from the study for the following reasons:

- Non-compliance with 5-day TMS treatment schedule. Patients must complete at least 4 consecutive days of treatment per week.
- It is the judgment of the investigator that the patient may be at risk for suicide
- The patient has rated a “yes” to question 4 or question 5 on the C-SSRS “Since Last Visit” version
- Patient meets relapse criteria (MADRS score  $\geq$  20 for two consecutive weeks
- Onset of manic or mixed symptoms
- Pregnancy
- Intercurrent illness, adverse event or any other reason concerning the well-being of the patient.

Patients who voluntarily withdraw from the study or who are discontinued from the study will be asked to complete an early termination visit. The early termination visit will be done one week after study withdrawal. A MADRS and CGI will be performed by the investigator. Patients will be referred back to their treating psychiatrist for standard clinical care.

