### Secondary Efficacy Measures:

- HAMD-17

The 17-item Hamilton Depression Rating Scale will be used as a secondary rating scale. This scale weights the physical symptoms of depression more than the psychic symptoms (Hamilton, 1960).

- QIDS-SR16

The Quick Inventory of Depressive Symptoms-Self Rating is a 16 item scale in which patients evaluate the severity of their depression. It is able to give an impression from the patients' point of view as to whether or not they are improved and provides a contrast to the clinician-rated scales (Rush 2003).

- C-SSRS

The C-SSRS is a clinician-administered instrument that assesses suicidal ideation (Posner. The "baseline" version of the instrument will be administered at the screening visit. The "since-last-visit" version will be administered at all other visits.

- YMRS

The Young Mania Rating Scale is the most often used scale to assess the degree of manic symptoms a patient has (Young et al., 1978). This scale will be used to screen out patients in mixed or manic states at enrollment and will be used during the trial to assess if the TMS treatment may be inducing mania.

- CGI Severity and CGI Improvement

These are global assessment scales of the severity of a patient's illness on a seven-point scale and degree of change from baseline on a seven-point scale (Guy, 1976). The CGI improvement scale is often the most sensitive marker to recognize status change in patients.

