### **Statistical Methods**

- Sample Size

We are looking to collect sufficient data to demonstrate the efficacy and safety of TMS in bipolar depression. As this is an open label trial we will aim to treat 30 patients to achieve a reasonable sample size.

- Primary Efficacy Analysis

The primary outcome measure will be the percentage of patients who respond or remit after 30 to 35 treatments. We will subdivide patients based on the diagnosis of either bipolar I or bipolar II to compare effectiveness between those groups.

The other primary outcome will be the percentage of patients who meet criteria for onset of manic symptoms based on the YMRS. The patients will also be separated based on their diagnostic category.

- Secondary Efficacy Analysis

We will also look at the HAM-D and CGI to see the percentage of patients meeting response criteria.

For the patients meeting remission criteria, we will calculate the number of treatments required to achieve remission. Patients who only meet response criteria will be treated for 30 to 35 sessions.

Responders and remitters will also be followed for six months after the final treatment to see the durability of response. Percentage of patients' meeting relapse criteria will be calculated.

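### The primary safety percentage counts manic symptoms on the YMRS, so a patient withdrawn for manic or mixed symptoms can be a non-event for Hypothesis 3

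*Combined protocol and SAP*

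**What the plan says.** Statistical Methods, under Primary Efficacy Analysis, names two primary outcomes. The second is the safety outcome: "The other primary outcome will be the percentage of patients who meet criteria for onset of manic symptoms based on the YMRS". It is also to be shown by bipolar I and II. No cut-off, change score, duration, time window or denominator is given with it.

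The question it has to answer is set earlier. Aim 2 reads: "In particular to observe if these patients are at risk for changing from a depressive state to a mixed or manic state". Hypothesis 3 is that TMS can be given safely "without inducing a manic or mixed episode switch" in patients on adequate mood stabilisers.

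In Phase II the YMRS is rated weekly. Between ratings, "Any suggestion of mania or activation will be assessed by the study physician", who decides whether the patient can stay in the study. Patient Withdrawal lists "Onset of manic or mixed symptoms" as a reason for stopping, and the Phase II section adds: "Patients who are discontinued due to onset of manic or mixed symptoms will be followed until resolution of these symptoms". The early termination visit falls one week after withdrawal; the scales named for it are the MADRS and CGI.

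Secondary Efficacy Measures says that the YMRS serves at entry to screen out mixed or manic states, and that it "will be used during the trial to assess if the TMS treatment may be inducing mania". The only YMRS number in the text is the entry condition, "an YMRS score of less than 12".

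**The concern.** The outcome and the hypothesis use different definitions. The outcome refers to manic symptoms on a scale; the hypothesis refers to a manic or mixed switch. The trial's own way of recognising a switch, assessment by the study physician followed if necessary by withdrawal, is not connected to the outcome.

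Two kinds of patient could be lost from the numerator. One is withdrawn for a mixed presentation that does not reach whatever YMRS criterion is used. The other is withdrawn between weekly ratings and has no YMRS at or after onset. In both cases the clinical team has recognised the problem and acted on it, yet the plan does not say that the patient counts.

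This percentage is the planned answer to Hypothesis 3 in a study without a control group. A switch left out of the numerator can only lower the reported rate, that is, make the treatment look safer.

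**Working it through.** **Step 1. The definitions side by side.**

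| Place | State covered | How it is established |
|---|---|---|
| Aim 2 | Mixed or manic | Not stated |
| Hypothesis 3 | Manic or mixed switch | Not stated |
| Study Overview, withdrawal | Activation suggesting mania or a mixed state | No YMRS score given |
| Phase II | Mania or activation; discontinuation for manic or mixed symptoms | Study physician; no YMRS score given |
| Patient Withdrawal | Manic or mixed symptoms | Investigator; no YMRS score given |
| Statistical Methods, primary outcome | Manic symptoms | A YMRS criterion that is not stated |

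Only the last row feeds the primary percentage, and no sentence connects the rows above to it.

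**Step 2. Can a withdrawn patient lack a qualifying YMRS?** The YMRS is weekly, while treatment is given five days a week. A patient stopped between ratings next has the early termination visit, one week later, for which the text names the MADRS and CGI. Follow-up to resolution names no scale. A YMRS may be done, but the text does not require it. Table 1, the schedule of events, was not supplied and could list one.

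**Step 3. Size of one uncounted case.** The plan gives no expected switch rate and no precision target, so there is no figure of its own to reproduce. Inputs: N = 30 (Statistical Methods, Sample Size) and N = 30 + 20 = 50 (Study Population, two sites).

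- One case: 1/30 = 3.3 points; 1/50 = 2.0 points.
- Exact (Clopper-Pearson) 95% limits for x events in n: lower = Beta quantile at 0.025 with parameters (x, n − x + 1); upper = Beta quantile at 0.975 with parameters (x + 1, n − x). For x = 0 the lower limit is 0 and the upper is 1 − 0.025^(1/n), which gives 11.6% at n = 30 and 7.1% at n = 50.

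| Assumed missed cases | Rate if counted (95% CI) | Rate if not counted (95% CI) |
|---|---|---|
| 1 of 30 | 3.3% (0.1 to 17.2%) | 0% (0 to 11.6%) |
| 2 of 30 | 6.7% (0.8 to 22.1%) | 0% (0 to 11.6%) |
| 1 of 50 | 2.0% (0.1 to 10.6%) | 0% (0 to 7.1%) |
| 2 of 50 | 4.0% (0.5 to 13.7%) | 0% (0 to 7.1%) |

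**Step 4. Chance of reporting zero events.** Let p be the true rate of manic or mixed switches and m the share that the YMRS rule misses. Both are assumptions. The chance of counting none is (1 − p(1 − m))^N.

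| N | p | m = 0 | m = 25% | m = 50% | m = 75% |
|---|---|---|---|---|---|
| 30 | 5% | 21.5% | 31.8% | 46.8% | 68.6% |
| 30 | 10% | 4.2% | 9.6% | 21.5% | 46.8% |
| 50 | 5% | 7.7% | 14.8% | 28.2% | 53.3% |
| 50 | 10% | 0.5% | 2.0% | 7.7% | 28.2% |

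For example, at N = 30, p = 5% and m = 50%: (1 − 0.025)^30 = 46.8%.

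**The case against.** The strongest reply is that the YMRS does see mixed states. The outcome counts symptoms, not a manic episode, and a patient can have manic symptoms while still depressed. The protocol itself relies on the YMRS to screen out mixed states at entry. This stands: a reader might infer that mixed cases are excluded from the outcome by design, and the documents do not support that. What remains is that nothing ensures they are counted.

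Second, while the criterion is unstated, nobody can say which withdrawn patients it would miss; a low threshold could count more patients than are withdrawn. This also stands. The point is therefore about what can happen under the plan, and Steps 3 and 4 are conditional on cases being missed.

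Third, a reader might infer that no YMRS is taken after withdrawal, or that a switch would disappear from view. Neither follows. Table 1 could list the rating, and the case would still appear as a withdrawal or adverse event; adverse event reports from both sites go to the DSMB and IRB. But no text carries those records into the primary percentage.

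Fourth, this is a small, descriptive, open-label study, and no test or limit is attached to this percentage. That lowers the severity. It does not close the gap between the outcome and Hypothesis 3.

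**Conclusion.** The point holds in this form: as written, a patient withdrawn for the event in Hypothesis 3 can be a non-event in the percentage that answers it. Each such case lowers the rate by 3.3 points at N = 30 or 2.0 points at N = 50, and a single one can turn a non-zero rate into zero. How many cases would be affected cannot be known from the documents; the missed cases, p and m above are all assumed.

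The missing YMRS criterion would by itself be a missing detail. It matters here because the clinical route to recognising a switch is not counted either.

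A reader might infer from the sponsor's earlier experience that so few switches are expected that one or two missed cases would be most of them. The documents do not support this. In the retrospective series, the statement that none met criteria for mania or a mixed state covers only the four patients stopped for side effects. The general statement under Rationale for Use of Mood Stabilizers concerns mania only. Neither fixes an expected rate or caps the count.

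This should be fixed, but it is not fatal to the study, because the cases remain visible outside the primary percentage.

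**What to change.** In Statistical Methods, define the primary safety event as either of:

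- (a) meeting a YMRS criterion that the sponsor fixes before any data review; or
- (b) withdrawal during Phase II for manic or mixed symptoms, whatever the YMRS score.

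State the window as the treatment phase and the denominator as all patients with at least one TMS session. Give the percentage with an exact 95% CI, overall and for bipolar I and II. Report (a) and (b) separately, so that the YMRS-only rate remains visible to a reader who prefers it. Reconcile the planned 30 patients in Statistical Methods with the 30 plus 20 in Study Population, since the precision depends on it.

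The cost is wording in one paragraph. Withdrawal reasons are already part of the trial, so (b) needs no new assessment, and clinical management does not change. There are downsides: the reported rate may be higher, and (b) may include symptoms short of an episode and rests on open-label judgement. Reporting the components separately makes both visible. A patient with emerging symptoms who is kept in the study would count only through (a); such cases would still be found among the adverse events.

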### **Study Population**

It is estimated that up to approximately 30 patients will participate in the study at the Sheppard Pratt site with 20 additional patients enrolling at the Mayo Clinic Rochester site. Patients must have Bipolar I or Bipolar II depression as defined by the Diagnostic and Statistical Manual of Mental Disorders (DSM-5 criteria) and be taking a mood stabilizer acceptable to the principal investigator. They will not be allowed to take antidepressant medication. Their depression must be at least moderate in severity without significant symptoms of activation or mania.

Patients treated may come from the Retreat assisted living, outpatient services, outpatient practices of local psychiatrists, the Sheppard Pratt day hospital, or inpatient units. Patients enrolled at Mayo Clinic will come from their Mood program, Mood Clinic, Inpatient practice and the community. It is unlikely that current inpatients will qualify for this study as most of them will have co-morbidities, psychotic symptoms or mixed presentations which would exclude them.

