### Rationale for Use of Mood Stabilizers

The goal is to make this study as naturalistic as possible. Clinical experience to date is that we have not seen TMS treated bipolar patients becoming manic but there is some risk of activation. Patients with bipolar type I will require mood stabilization within the clear therapeutic range. As there is no clear evidence for what bipolar II patients require for adequate stabilization, the criteria for adequate treatment will be more liberal and patient specific at the discretion of the principal investigator.

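### The only planned safety result, a manic-onset percentage on the YMRS, leaves out patients withdrawn for activation or mixed symptoms below the cut-off and any YMRS rise short of onset

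*Combined protocol and SAP*

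**What the plan says.** The safety aim has two parts. It opens broadly, "To investigate the safety of TMS in a population at risk for activation from neuromodulation", and then narrows: "In particular to observe if these patients are at risk for changing from a depressive state to a mixed or manic state". Hypothesis 3 is that TMS can be given safely "without inducing a manic or mixed episode switch". The rationale for mood stabilizers treats mania and activation as different things: "we have not seen TMS treated bipolar patients becoming manic but there is some risk of activation".

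Activation is kept out at entry ("Their depression must be at least moderate in severity without significant symptoms of activation or mania", with a YMRS below 12) and watched for during treatment. Patients are assessed "once per week for severity of depression and evidence of any symptoms suggestive of mania or agitation", the YMRS is rated weekly, and the study physician evaluates any suggestion of mania or activation. The Study Overview adds: "Patients will be withdrawn for safety concerns, particularly the onset of activation suggestive of mania or a mixed state". Patient Withdrawal lists manic or mixed symptoms as a reason to discontinue. Adverse events are recorded and go to the DSMB and the IRB.

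Statistical Methods turns this into one result: "The other primary outcome will be the percentage of patients who meet criteria for onset of manic symptoms based on the YMRS", overall and by diagnosis. The secondary analyses are response on the HAM-D and CGI, number of treatments to remission, and relapse.

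**The concern.** There are two routes to a manic, mixed or activated outcome in this trial: a YMRS score that meets a criterion, and a clinician's decision to stop treatment. Only the first feeds a planned result. If the two disagree, the patient most worth reporting, someone taken off TMS because of activation or mixed symptoms, is counted with the patients who had no problem.

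The site's own experience leads one to expect few or no manic onsets. A percentage near zero is then the likely headline, and Statistical Methods says the trial is meant to demonstrate safety. A reader could take that figure as the full account of activation, when the plan yields no figure for activation as such.

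**Working it through.** **1. Planned results.** Statistical Methods contains one YMRS analysis, the onset percentage. It contains no count of withdrawals by reason, no adverse event summary, and no summary of YMRS change or peak.

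**2. Outcome against Hypothesis 3.** The hypothesis covers manic or mixed switches; the outcome covers manic symptoms on the YMRS. Response (MADRS fall of at least 50%), remission (MADRS below 10) and relapse (MADRS 20 or more for two consecutive weeks) all have rules. Manic onset has none: no cut-off, change, duration or confirmation. The only YMRS number is the entry limit of 12. (Only the titles of Table 1 and the appendices were available for this check.)

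**3. A withdrawn patient, traced.** The YMRS is weekly and the withdrawal decision is clinical. The early termination visit, one week later, names the MADRS and CGI but not the YMRS. A patient stopped between ratings, or with mixed symptoms that score below the cut-off, therefore need not have a qualifying YMRS and is a non-event.

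**4. A patient who rises but stays on treatment.** Entry requires a YMRS below 12. A patient who peaks at 14 has passed that limit, yet at any onset cut-off above 14 is reported like a patient with no change.

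**5. What the withdrawal route could change.** Statistical Methods aims for n = 30; Study Population gives about 30 + 20 = 50 over two sites. With no onsets the exact two-sided 95% upper limit is 1 − 0.025^(1/n):

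- n = 30: 11.6%
- n = 50: 7.1%

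Suppose that, with no onsets, 1, 2 or 3 of 30 patients are withdrawn below the cut-off (assumed counts). The plan reports 0/30 each time. A combined count gives (exact 95% CI):

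- 1/30 = 3.3% (0.1% to 17.2%)
- 2/30 = 6.7% (0.8% to 22.1%)
- 3/30 = 10.0% (2.1% to 26.5%)

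**6. Rises short of onset: illustration only.** The documents give no YMRS mean or SD, and the cut-offs 16 and 20 are assumptions. Simulated trials had n = 30, one baseline rating kept only if below 12, and six weekly ratings, rounded and floored at 0. The three assumed input sets, with equal between-patient and week-to-week SD, were A (mean 2, SDs 1.5), B (mean 4, SDs 2.5) and C (mean 6, SDs 3). Entries are percentages of trials, A / B / C, with simulation error of about 1 point.

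| Assumed true pattern | No patient reaches 16 | 95% CI for mean change above 0 |
|---|---|---|
| All patients rise 2 points | 100 / 64 / 3 | 100 / 98 / 99 |
| 20% of patients rise 5 | 99.9 / 45 / 4 | 56 / 42 / 57 |
| 10% have one week at +10 | 86 / 34 / 7 | 9 / 8 / 18 |

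For the 2-point rise, no patient reaches 12 in 97 / 0.1 / 0% of trials, and no patient reaches 20 in 100 / 99 / 78%. With no true rise, set C still has no patient at 16 in only 34% of trials, so onsets there are partly noise. The mean change misses short spikes, which is why peaks are also needed.

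The added summaries have their own noise. With no true rise, 0 / 7 / 27% of patients reach 12, the mean peak change is +1.7 / +3.0 / +4.1 points, and the CI for mean change lies above 0 in 3 / 4 / 12% of trials.

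**The case against.** The strongest reply is that activation is not a separate question. In the safety aim it describes the population; the question posed is change to a mixed or manic state, and no hypothesis concerns lesser activation. This stands in part: a yes/no switch outcome is a reasonable choice for the aim. But the rationale section separates activation from mania, and mixed states are named in both the aim and Hypothesis 3 while the outcome omits them.

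Second, activation is already handled by physician assessment, withdrawal, adverse event recording and DSMB and IRB review. A reader might infer from the gap that activation goes unmonitored or will never be reported. The documents do not support that. Statistical Methods is also not exhaustive: it omits the MADRS change score that the efficacy section calls primary. Oversight is nonetheless not a planned result.

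Third, activation short of onset has no boundary until onset is defined. If the cut-off were 12 with no duration rule, a count of scores of 12 or more would repeat the onset count. This stands, and it is why the point is tied to the cut-off. It does not affect withdrawals on clinical judgment.

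Fourth, mean change and crossings of 12 do not by themselves show activation, and the simulated 2-point rise is not something any document calls activation. This also stands, and it argues for a short descriptive addition rather than a test.

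**Conclusion.** The concern holds in a limited form and is minor. Followed as written, the plan reports a patient withdrawn for activation or mixed symptoms below the YMRS cut-off as having no event, and gives no result for smaller rises.

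A reader might infer that the onset percentage settles Hypothesis 3 and that only mild activation is left out. The documents do not support that, because the onset criteria are unstated and mixed episodes are not covered. Nor can one claim that a known share of activation would be missed. Across the assumed inputs and cut-offs, the chance that a uniform 2-point rise produces no onset at all runs from 0% to 100%. The conclusion rests on the text: one YMRS result, two routes to withdrawal or onset, and only one of them counted.

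**What to change.** Keep the onset percentage, with its cut-off stated as a separate matter, and add to Statistical Methods:

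> For all patients with at least one TMS session we will report, overall and for bipolar I and II: (a) the number and percentage, with exact 95% CI, who met the YMRS onset criteria, or were withdrawn for activation, manic or mixed symptoms, or had activation recorded as an adverse event, with each component also shown separately; and (b) descriptively, the change from the last pre-TMS YMRS to the mean on-treatment YMRS, each patient's peak on-treatment YMRS, and the number with any on-treatment YMRS of 12 or more.

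Patients without an on-treatment YMRS stay in the denominator of (a) and are listed as missing in (b). No pass/fail margin is needed.

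The cost is a few sentences and two summaries of scores, withdrawal reasons and adverse event notes that the protocol already calls for, with no new visit or rating. The downsides are a possibly less favourable safety statement, some chance crossings of 12, and a small upward bias in mean change from the entry ceiling (+0.0 / +0.1 / +0.4 points under the assumed inputs with no true rise). Without a control arm, no change can be attributed to TMS, and the report should say so.

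### The manic-onset primary outcome rests on a weekly YMRS alone, so a switch that ends treatment off-schedule, or a mixed switch below the YMRS criterion, could go uncounted

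*Combined protocol and SAP*

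**What the plan says.** Under Statistical Methods, Primary Efficacy Analysis, the second primary outcome reads: "The other primary outcome will be the percentage of patients who meet criteria for onset of manic symptoms based on the YMRS". It is also to be split by bipolar type. The only YMRS number in the visible text is the entry limit of below 12 (Inclusion and Exclusion Criteria – Phase II, inclusion 3).

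On measurement, the Phase II section says "YMRS, the C-SSRS (Columbia Suicide Severity Rating Scale) and CGI-S will be performed once per week". Between ratings, "Any suggestion of mania or activation will be assessed by the study physician", who decides whether the patient can stay in the study. No scale is named for that assessment.

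On withdrawal, the Study Overview says "Patients will be withdrawn for safety concerns, particularly the onset of activation suggestive of mania or a mixed state". Patient Withdrawal lists "Onset of manic or mixed symptoms" among the reasons for which the investigator may discontinue a patient. Neither place ties the decision to a YMRS score.

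After withdrawal, the same section says: "The early termination visit will be done one week after study withdrawal. A MADRS and CGI will be performed by the investigator". The Phase II section adds: "Patients who are discontinued due to onset of manic or mixed symptoms will be followed until resolution of these symptoms". It names no scale for that follow-up and no rule for carrying the case into the primary percentage.

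**The concern.** Hypothesis 3 is that TMS can be given without a switch into mania or a mixed episode. The outcome that tests it names manic symptoms only and reads them from one scale. The decision to stop a patient for the same kind of event is made on clinical grounds. The two need not agree.

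A patient could have a low weekly YMRS, switch some days later, be withdrawn by the physician, and have no YMRS that meets any criterion. Read literally, the outcome does not count that patient. Mixed switches have a further problem. The protocol says of the YMRS "This scale will be used to screen out patients in mixed or manic states at enrollment", so it may catch some of them, but one scoring below the onset criterion would be missed even though the hypothesis covers it.

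The error runs one way. An uncounted switch can only lower the reported rate, and a low rate is what supports the hypothesis. With few events expected, a single case can decide whether the study reports no switches at all. Without a written rule, that case would be classified after it is known, in an open-label study.

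**Working it through.** The plan states no expected switch rate, precision target or calculation for this outcome, so there is no figure to reproduce. The check has a textual part and an arithmetic part.

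**1. Can a switch escape the count?**

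| Step | Basis in the visible text | YMRS required? |
|---|---|---|
| Scheduled rating | Weekly (Phase II) | Yes |
| Suspected mania between ratings | Study physician assesses (Phase II) | Not stated |
| Withdrawal | Clinical judgement (Study Overview; Patient Withdrawal) | Not stated |
| Early termination, one week later | MADRS and CGI (Patient Withdrawal) | Not named |
| Follow-up to resolution | Phase II | Not named |
| Counted as an event | YMRS criterion (Statistical Methods) | Cut-off not given |

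Nothing in the chain guarantees a YMRS during the episode. The text permits three treatments of such a patient: event, non-event, or exclusion from the denominator. With no other events at n=30, the last two give 0/30 and 0/29, both 0%, against 1/30 = 3.3% if the case is counted.

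**2. Effect of one uncounted case.** If the patient stays in the denominator, the rate falls by 1/n.
- n=30 (Statistical Methods, Sample Size): 1/30 = 3.3 points.
- n=50 (Study Population, 30 + 20): 1/50 = 2.0 points.
- Bipolar-type subgroup of 15 (assumption: even split of 30; the plan gives no split): 1/15 = 6.7 points.

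**3. Exact (Clopper-Pearson) 95% intervals.** The lower limit is the 0.025 quantile of Beta(x, n−x+1), or 0 when x=0. The upper limit is the 0.975 quantile of Beta(x+1, n−x).

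| Events | n=30 | n=50 | n=15 (assumed) |
|---|---|---|---|
| 0 | 0% (0 to 11.6) | 0% (0 to 7.1) | 0% (0 to 21.8) |
| 1 | 3.3% (0.1 to 17.2) | 2.0% (0.1 to 10.6) | 6.7% (0.2 to 31.9) |
| 2 | 6.7% (0.8 to 22.1) | 4.0% (0.5 to 13.7) | – |

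**4. Chance of reporting zero switches.** Let p be the true rate and m the share of switches that go uncounted. Both are assumptions. The chance is (1 − p(1−m))^n. For p=5%, m=50%, n=30 this is (1 − 0.025)^30 = 46.8%, against (1 − 0.05)^30 = 21.5% with none missed.

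| True rate, n | None missed | 25% missed | 50% missed | 80% missed |
|---|---|---|---|---|
| 5%, n=30 | 21.5% | 31.8% | 46.8% | 74.0% |
| 5%, n=50 | 7.7% | 14.8% | 28.2% | 60.5% |
| 10%, n=30 | 4.2% | 9.6% | 21.5% | 54.5% |
| 10%, n=50 | 0.5% | 2.0% | 7.7% | 36.4% |

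This table shows direction and sensitivity. It does not forecast how many cases will be missed.

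**The case against.** Several points on the other side carry weight.

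- **The window is narrow.** The Phase II section also schedules the check for manic or agitated symptoms once a week, the same frequency as the YMRS. A switch found at the planned check should normally have a rating from that week. Off-schedule detection remains possible, since patients attend five times a week and are asked about side effects at each visit, but it is not the planned route. This stands, and it lowers the likely number of cases.
- **Switches look rare.** Background reports 45 bipolar patients treated at the site. Four were stopped for side effects, and none of those four met criteria for mania or a mixed state. The rationale for mood stabilizers says the site has seen no manic switches. These data are retrospective and incomplete (five patients finished elsewhere, two had incomplete data), but they are the only evidence on frequency in the documents. This also stands.
- **Some content is not shown.** A reader might infer that the plan has no onset cut-off and no YMRS at early termination. Table 1 and the YMRS appendix are not visible and could hold either, so the claim is limited to the visible text. A rating one week after withdrawal could still miss an episode already treated or resolving.
- **Not every such withdrawal is a switch.** A reader might infer that all withdrawals for manic or mixed symptoms, or any start or increase of antimanic treatment, should count as events. The documents do not support that. The Study Overview allows withdrawal on activation that is only suggestive, so this would replace a possible under-count with an over-count.
- **The event would be known.** It would be assessed by the physician, followed to resolution, and reviewed as an adverse event by the DSMB and IRB. That protects the patient, but it does not bring the case into the primary percentage.

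**Conclusion.** The point holds in a limited form. On the visible text, the manic-onset percentage can omit a manic switch that leads to withdrawal between weekly ratings, or a mixed switch below the YMRS criterion. Any omission favours Hypothesis 3.

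A reader might go further and infer that such patients are excluded by rule, or that many would be missed. The documents support neither: they are silent on how to count these patients, and the weekly mania check and the site's experience point to few cases.

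The shift of 3.3 points (n=30) or 2.0 points (n=50) per case assumes the patient stays in the denominator as a non-event. The subgroup figures assume 15 patients, and the zero-event probabilities rest on assumed rates and missed shares. The change is worth making before results are known, because it is cheap and one case can separate a report of no switches from a report of one. Confidence is medium, given the unseen schedule and appendices.

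**What to change.** 1. In Statistical Methods, state the YMRS cut-off that defines onset of manic symptoms.
2. Require a YMRS when the study physician assesses suspected mania or activation, at withdrawal for that reason, and at the early termination visit.
3. Keep the YMRS percentage. Beside it, report the percentage of patients who meet the cut-off OR are withdrawn with a manic, hypomanic or mixed episode that the study physician has confirmed against DSM-5 criteria. Use all treated patients as the denominator, with exact 95% confidence intervals overall and by bipolar type.
4. List withdrawals for activation short of an episode separately, and do not count them as switches. Do not make a change in antimanic treatment a component of the outcome.

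The cost is a few sentences and a small number of extra ratings. The reported rate may be slightly higher. The added component relies on clinical judgement in an open-label study, which is why the YMRS percentage should stay visible on its own.
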